**TITLE OF THE PROTOCOL: RAMAN SPECTROSCOPY AND
COLORECTAL CANCER: TOWARDS EARLY DIAGNOSIS AND
PERSONALISED MEDICINE**

Short title/Acronym: Raman spectroscopy and colorectal cancer

Sponsor:

Representative of the Sponsor:

[name]
R&D Manager
R&D Department
Morriston Hospital
Swansea
[name]

REC reference: 14/WA/0028

STUDY SUMMARY/SYNOPSIS

TITLE	Raman spectroscopy and colorectal cancer: towards early diagnosis and personalised medicine
SHORT TITLE	Raman spectroscopy and colorectal cancer
Protocol Version Number and Date	ABM/RS/v4 Version 4;08/2/2017
Methodology	Prospective cohort observational study
Study Duration	5 years 6 months
Study Centre	ABM University LHB and Swansea University
Objectives	To explore the feasibility of detecting presence of differing stages of colorectal cancer at different phases of treatment using Raman spectroscopy
Number of Subjects/Patients	1,800 across 8 study groups
Main Inclusion Criteria	Stage T3/4 colorectal cancer (group 1) n=300 T1/2 early colorectal cancer (T1/2) from Bowel Screening Wales programme (group 2) n=300 Benign colorectal polyps (>1cm size)(group 3) n=200 Matched controls (without history of inflammatory bowel disease or familial bowel cancer)(group 4) n=300 Locally advanced rectal cancer requiring chemoradiotherapy (group 5) n=80 Bowel cancer patients at high risk of developing metastatic disease (group 6) n=20 Patients diagnosed with other cancer types (e.g. lung, pancreas)(group 7) n=300 Patients in primary care with colorectal symptoms (group 8) n=300
Statistical Methodology and Analysis	Principal Components Analysis (PCA) and hierarchical cluster analysis to measure accuracy, sensitivity and specificity measures for each patient group.

Protocol Agreement Page

The clinical study as detailed within this research protocol (**Version 2, dated 9th May 2014**), or any subsequent amendments will be conducted in accordance with the Research Governance Framework for Health & Social Care (2005), the World Medical Association Declaration of Helsinki (1996) and the current applicable regulatory requirements and any subsequent amendments of the appropriate regulations.

Chief Investigator Name: [name] [name] (Consultant Surgeon)

Chief Investigator Site: Singleton Hospital, Swansea

Contact details: [contact]
 Email: [contact]
 Fax:

Signature and Date:

Statistician Name: [name], Swansea Trials Unit

Contact details: Tel No:
 Email:[contact]
 Fax:

Signature and Date:

1.1 Background

Colorectal cancer (CRC) remains one of the leading causes of cancer related death in the Western world. Early diagnosis, the principle behind the UK bowel cancer screening programme, is pivotal to optimise outcomes. Current screening methods are invasive, have low specificity for cancer and do not have widespread patient acceptance. As such there is a pressing need to develop alternative non-invasive acceptable methods of screening for bowel cancer.

There are 14,000 new cases of rectal cancer each year in the UK, many being treated by combined chemotherapy and radiotherapy (RT) to reduce tumour size before surgery. Response to chemoradiotherapy is highly variable and some patients do not respond. Such patients endure the side effects of treatment, including poor bowel function, incontinence, sexual dysfunction and impaired quality of life, without clinical gain.

Whilst high levels of pathological tumour regression in response to RT is desirable and is associated with significantly improved disease free survival (Rödel 2005), in practice a spectrum of response is observed, ranging from complete pathological response to disease progression through treatment resistance. The broad application of RT additionally exposes patients with radiation-resistant disease to long term complications, which includes incontinence, sexual dysfunction and impaired wound healing. An accurate biologically based method is needed to stratify patients in predicting response to RT and rationalising it to those set to experience clinical gain, with alternative treatments for predicted non-responders.

Plasma and faeces of colorectal cancer patients is known to contain various proteomic and metabolomic markers together with circulating tumour cells (CTCs) characterised by specific surface markers. Faecal samples are known to contain shed CRC cells and mutated DNA (Calistri 2010). Equally, tissue biopsies from a variety of human malignancies have been demonstrated as having unique spectra which can be exploited for in-situ diagnosis (Mavarani, 2013).

Raman spectroscopy is an established technology based upon the spectroscopic analysis of inelastically scattered light for changes that reflect the molecular and structural composition of the biological sample under investigation. The resultant Raman spectrum directly reflects the molecular composition of the interrogated sample which may be considered unique for individual disease states, including certain cancer types. Raman therefore has potential not only as a diagnostic tool for the identification of malignancy, but also for personalised cancer medicine, disease monitoring and even nanoparticle-targeted delivery of chemotherapeutics.

This exploratory work will begin to establish a signature based on the molecular composition of different stages of colorectal carcinogenesis. The likely benefits of the proposed research to patients include a more acceptable means of screening for colorectal cancer. Present unmet needs affecting surgical and oncological treatment of CRC patients is the need for improved prognostication to allow personalised treatment of CRC, for example to select patients for adjuvant chemotherapy after surgical resection based on persistent plasma markers of cancer activity, and to predict the response of locally advanced rectal cancer to chemoradiotherapy.

As colorectal cancer is such a high profile condition, positive results will be of enormous public interest, particularly if a simple blood test could predict an individual's risk of having bowel cancer. As such the study will enrol patients from primary care with colorectal symptoms/signs towards reducing the requirement for invasive diagnostic tests.

1.2 Preclinical Data

Early reports have suggested specific Raman parameters in the serum of colorectal cancer patients (Li , Applied Optics 2012), whilst Lin et al (Lin, Optics Express 2011) have had some initial successes at implementing gold nanoparticle enhancement of Raman from blood serum. Circulating stem cells (CSCs) and tumour cells (CTCs) are both present in the peripheral blood of patients at all stages of malignancy, and can be characterised by both specific surface markers (EpCAM, CD44, MUC-1, CK20, CEA) and mutated driver genes (KRAS, BRAF, PIK3CA). It is reported that SERS nanoparticles functionalized with epidermal growth factor receptor (EGFR) affibodies preferentially target EGFR-positive cell line tissues (Jokerst 2011).

Raman scattering suffers from the disadvantage of poor scattering efficiencies due to the small scattering cross-section. This problem can be eased by the use of nanoparticles to act as enhancing agents. The very recent literature is exploiting the effects of nanoparticles at producing enhanced spectra to refine detection sensitivity and specificity.

1.3 Rationale and Risks/Benefits

Blood sampling will involve an invasive blood test with has the attendant risks of pain, local bruising and infection. These risks will be minimised as blood sampling will be done by experienced practitioners using aseptic technique. A faecal sample will be collected by the patient which may cause intrusion or distress. This will be minimised as the patient can collect the sample in the privacy of their own home.

As this is an exploratory study research participants will not gain personal benefit.

2. Trial Objectives and Design

2.1 Trial Objectives

[figure not shown]
Primary Objective – To determine if there is an association between Raman spectral signature and presence of colorectal malignancy.

Primary Endpoint-Detection of surface enhanced nanoparticles in samples from colorectal cancer patients

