3.1 Number of Subjects and Subject Selection

Paired plasma, faecal samples will be obtained from 300 patients with advanced colorectal cancer (stage T3/4) prior to surgical treatment (group 1). Plasma samples only will be obtained from 300 early colorectal cancers (T1/2) from the Bowel Screening Wales programme (group 2), 200 patients with benign colorectal polyps (>1cm size)(group 3) and 300 matched controls (without history of inflammatory bowel disease or familial bowel cancer)(group 4). The programme of work will be expanded to include 80 patients with locally advanced rectal cancer requiring chemoradiotherapy (group 5) who will have samples taken at diagnosis, during and after chemoradiotherapy and after resection of their tumour to identify changes in the spectra at each stage of treatment. Spectra can be compared with pathological factors, including tumour regression grade as a response to chemoradiotherapy, to establish if spectral analysis before CRT can predict the degree of downstaging seen. A further group of interest will be those at high risk of developing metastatic disease (group 6), for example colorectal cancers of advanced stage demonstrating adverse pathological features such as lymphovascular invasion or lymph node metastases. These twenty patients will have serial blood tests performed at five time-points over a 2 year follow up period, in parallel with standard investigations such as radiological imaging and tumour marker analysis. This aims to detect spectral change which predates development of liver or lung metastases on standard imaging modalities. This would have the potential of diagnosing metastatic disease at a pre-clinical stage affording earlier access to treatment. To establish if the spectral signatures are specific to colorectal cancer, a group of 300 patients diagnosed with stage-matched non-colorectal cancers (for example, lung cancer, pancreatic cancer, prostate cancer, endometrial cancer) will be studied with a single blood test for comparison.

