Towards utilising the blood test as a means of discriminating between patients with colorectal cancer and those without we wish to obtain blood samples from 300 patients in primary care with colorectal symptoms and compare the test result (positive, equivocal or negative) with their final diagnosis (colorectal cancer or benign pathology). The blood test results will not be revealed to the GP or the patient so cannot influence the current referral pathway until the blood test is validated for this patient population. We will use this data to plan a subsequent interventional study.

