4.3 Schedule of assessment for each visit

Blood sampling- a 5mL blood sample will be obtained from the participant. Serum will be obtained by centrifugation at 3,000 rpm for 10 min and stored at 4°C until analysed. Alternatively the serum may be stored at -80 degrees C until analysis.

Faecal samples will be collected by participants onto the spatula within in a 5mL faecal collection universal container. Samples will be stored at 4°C and will be analysed within 3 days to prevent degradation. Samples will be serially diluted prior to analysis to optimize wavelength detection.

Samples will be subject to Raman analysis with the aim of optimising excitation wavelength and spectral reproducibility. The Raman system (InVia Renishaw) is capable of both 785 nm and 532 nm studies. Comparisons across different patient groups will help determine the best wavelength conditions for reliable data acquisition, sample handling and data reproducibility. Unlike previous published studies, laser power degradation effects on the sample will be tested, as reproducibility is key in identifying the origins of spectral differences from the patient groups. To overcome the inefficiency of Raman scattering it is proposed that through using multiplexed surface-enhanced Raman scattering (SERS) gold nanoparticles functionalised to specific surface markers a unique spectral pattern will be identified. We will analyse blood, faeces and the reference biopsy sample with combinations of functionalised Ag-nanoparticles (labelled with EpCAM, CD44, MUC-1, CK20, CEA) and analyse the resultant spectral peaks and be compared to positive controls. These tests will give unique insight into the potential diagnostic ability of Raman spectroscopy for colorectal cancer.

To optimise the nanoparticle functionalisation and SERS detection an initial programme of work will study the blood, tissue and faecal samples from patients with advanced disease and establish the optimal antibody pairing from a potential panel of five antibodies associated with colorectal cancer cells.

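### The primary endpoint in section 2.1 does not measure the primary objective: it names the nanoparticle signal and is confined to cancer patients, so it has no comparator

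*Protocol*

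**What the plan says.** Protocol section 2.1 gives the primary objective as "To determine if there is an association between Raman spectral signature and presence of colorectal malignancy". It then states "Primary Endpoint-Detection of surface enhanced nanoparticles in samples from colorectal cancer patients". No other legible part of the protocol restates or qualifies the primary endpoint.

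Section 4.3 explains where the nanoparticles come from. The laboratory applies them to the samples: "We will analyse blood, faeces and the reference biopsy sample with combinations of functionalised Ag-nanoparticles". Their purpose is to produce a spectrum, in that by "using multiplexed surface-enhanced Raman scattering (SERS) gold nanoparticles functionalised to specific surface markers a unique spectral pattern will be identified". (The section names both gold and silver particles; nothing here turns on that.)

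The rest of the protocol is built around comparison:

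- **Section 3.1** recruits 200 polyp patients (group 3), 300 matched controls (group 4) and 300 patients with other cancers (group 7), the last for this reason: "To establish if the spectral signatures are specific to colorectal cancer, a group of 300 patients diagnosed with stage-matched non-colorectal cancers". It also sets a three-level test result against final diagnosis in 300 symptomatic primary-care patients (group 8).
- **Section 7.1** justifies 300 per subgroup by a target above 85% for both sensitivity and specificity, in an independent validation test set.
- **Section 7.2** compares spectra between patient groups by principal components and cluster analysis, leading to accuracy, sensitivity and specificity.

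The synopsis words the objective more broadly: "To explore the feasibility of detecting presence of differing stages of colorectal cancer at different phases of treatment using Raman spectroscopy".

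**The concern.** An endpoint has to be the variable, in the people, from which the objective can be judged. This one departs from its objective twice. The variable is detection of an added particle, where the objective speaks of a spectral signature. The population is cancer patients only, where an association needs the same measurement in people without colorectal malignancy.

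The primary endpoint is the sentence against which success is declared. As it stands, a favourable result would not show that the signature distinguishes cancer from no cancer. The quantities that would show it, sensitivity together with specificity, have no primary status. That leaves room to choose the real primary outcome after spectra have been seen. The risk is practical here: the wavelength and antibody pairing are still to be optimised (4.3), and the classification algorithms are still to be developed (7.2).

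**Working it through.** **Step 1. Set the passages side by side.**

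| Place | Variable | People | Quantity |
|---|---|---|---|
| 2.1 objective | Raman signature | With and without colorectal malignancy | Association |
| 2.1 endpoint | Nanoparticle detection | Colorectal cancer only | Detection rate |
| 3.1, group 8 | Test result | Symptomatic, cancer or benign | Agreement with diagnosis |
| 7.1 | Classification in a validation set | Diseased and non-diseased | Sensitivity, specificity |
| 7.2 | Raman spectra | Different patient groups | Accuracy, sensitivity, specificity |

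The endpoint row is the only one without a comparator.

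**Step 2. Who enters the endpoint.** Group sizes are from the synopsis and 3.1. Their total reproduces the stated figure: 300 + 300 + 200 + 300 + 80 + 20 + 300 + 300 = 1,800.

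- Colorectal cancer at entry (groups 1, 2, 5, 6): 300 + 300 + 80 + 20 = 700.
- Recruited without colorectal cancer (groups 3, 4, 7): 200 + 300 + 300 = 800. None of these enters the endpoint.
- Group 8 (300) is mixed, and the protocol gives no expected split.

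**Step 3. What a cancer-only result can show.** Take a detection rate of 85% in cancers, borrowing the 7.1 target for illustration. With Youden index J = detection rate in cancers − detection rate in controls:

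- control rate 15%: J = 0.85 − 0.15 = 0.70;
- control rate 50%: J = 0.85 − 0.50 = 0.35;
- control rate 85%: J = 0.85 − 0.85 = 0, no association.

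The endpoint takes the same value in all three cases. At best it gives a sensitivity.

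**Step 4. What the 300 per subgroup rests on.** Section 7.1 gives the 85% target, 80% power and 95% confidence, but no null and expected pair and no sidedness, so 300 cannot be strictly reproduced. As an assumption, treat it as a one-sample proportion:

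n = [z(α)·√(p0(1−p0)) + z(power)·√(p1(1−p1))]² / (p1−p0)²

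For p0 = 0.85, p1 = 0.90, one-sided 5%: (1.645 × 0.3571 + 0.8416 × 0.3000)² / 0.05² gives 283.

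| Null p0 | Expected p1 | n, one-sided 5% | n, two-sided 5% |
|---|---|---|---|
| 85% | 90% | 283 | 363 |
| 85% | 91% | 191 | 246 |
| 80% | 85% | 368 | 471 |
| 79% | 85% | 262 | 336 |
| 78% | 85% | 197 | 253 |

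At n = 300, the 85% against 90% case has power 82% one-sided (exact binomial 81%) or 71% two-sided (exact 69%). So 300 is plausible but not verifiable. In every row the proportion is a sensitivity or a specificity, and the specificity half of the justification has no counterpart in the endpoint.

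**Step 5. Can the planned groups support an endpoint that matches the objective?** Compare the test-positive rate in 300 cancers with 300 controls, two-sided 5%, by the normal approximation for two proportions.

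- 85% against 15% positive (85% sensitivity and specificity): power above 99.9%; about 7 per group would give 80%.
- Around a 50% positive rate, a difference of 11.5 points has 80.6% power.
- Precision of an observed 85% with n = 300: 1.96 × √(0.85 × 0.15 / 300) = 0.040, a half-width of 4.0 points.

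The groups are large enough. The 4.0 points assumes that all 300 serve as validation samples; if some are used to build the classifier, the interval widens.

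**The case against.** **A reader might infer that the trial cannot answer its own question.** The protocol does not support that. Controls, polyps and other cancers are sampled, group 8 has its result compared with diagnosis, 7.2 plans a between-group spectral comparison, and 7.1 is framed on sensitivity and specificity. The data could meet the objective.

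**The reagent point can be pressed too far.** The particles are to be functionalised to five named surface markers, with peaks compared to positive controls, and section 1.2 cites preferential targeting of marker-positive tissue. The natural reading of detection is a signal from marker-bound particles, which does depend on the sample. A reader might infer that the endpoint would be met in every sample, cancer or control; nothing in the protocol says that the particles bind non-specifically. This softens the complaint about the variable. It leaves the missing comparator untouched.

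**The synopsis objective might be read as a rival objective.** It is better read as a broad feasibility summary that takes in the serial groups 5 and 6. It should be aligned with 2.1, but it is not a contradiction of weight.

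**The study calls itself exploratory, and an analysis plan may exist.** That lowers the stakes, but an analysis plan works from the protocol's endpoint, and a silent substitution there would not repair a primary endpoint that the protocol states wrongly. A figure under 2.1 is not visible in the text reviewed and may hold more; the legible endpoint sentence is complete and faulty as it stands.

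**Conclusion.** The point holds as a fault in the endpoint definition. As written, the 2.1 primary endpoint cannot show an association and cannot give a specificity, and it does not match the basis of the sample size or the planned analysis. This follows from the text and does not depend on any assumed rate. The 85% detection rate and the control rates in the working are illustrations, and the sample-size figures rest on assumed null and expected values.

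The conclusion stops at the definition. Neither the recruitment nor the group sizes nor the between-group comparison needs to be redesigned for this reason. Because the sentence decides what counts as the primary result, it should be corrected before any primary analysis.

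**What to change.** Amend section 2.1 so that the primary endpoint is the signature-based classification (or spectral score) of each patient's blood sample against diagnosis, compared between colorectal cancer (groups 1 and 2) and non-cancer controls (group 4). Report sensitivity and specificity with 95% CIs.

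- **Validation.** State that these estimates come from the independent validation set named in 7.1, not from samples used to choose wavelength, antibody pairing or PCA loadings.
- **Sample type.** Use blood, because faeces are collected only in group 1 and so have no control.
- **Equivocal results.** Fix their handling in advance. Counting them as positive raises sensitivity and lowers specificity, and counting them as negative does the reverse. Either can be defended; the choice belongs to the investigators.
- **Nanoparticle signal.** Keep its detection as a technical feasibility endpoint.
- **Other groups.** List groups 3 and 5 to 8, stage and treatment phase as secondary comparisons.
- **Synopsis.** Align its objective with 2.1.

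The cost is one protocol amendment, with no new patients, samples or tests.

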2.2 Trial Design

Cohort observation study

2.3 Study Scheme Diagram

3. Subject Selection

3.1 Number of Subjects and Subject Selection

Paired plasma, faecal samples will be obtained from 300 patients with advanced colorectal cancer (stage T3/4) prior to surgical treatment (group 1). Plasma samples only will be obtained from 300 early colorectal cancers (T1/2) from the Bowel Screening Wales programme (group 2), 200 patients with benign colorectal polyps (>1cm size)(group 3) and 300 matched controls (without history of inflammatory bowel disease or familial bowel cancer)(group 4). The programme of work will be expanded to include 80 patients with locally advanced rectal cancer requiring chemoradiotherapy (group 5) who will have samples taken at diagnosis, during and after chemoradiotherapy and after resection of their tumour to identify changes in the spectra at each stage of treatment. Spectra can be compared with pathological factors, including tumour regression grade as a response to chemoradiotherapy, to establish if spectral analysis before CRT can predict the degree of downstaging seen. A further group of interest will be those at high risk of developing metastatic disease (group 6), for example colorectal cancers of advanced stage demonstrating adverse pathological features such as lymphovascular invasion or lymph node metastases. These twenty patients will have serial blood tests performed at five time-points over a 2 year follow up period, in parallel with standard investigations such as radiological imaging and tumour marker analysis. This aims to detect spectral change which predates development of liver or lung metastases on standard imaging modalities. This would have the potential of diagnosing metastatic disease at a pre-clinical stage affording earlier access to treatment. To establish if the spectral signatures are specific to colorectal cancer, a group of 300 patients diagnosed with stage-matched non-colorectal cancers (for example, lung cancer, pancreatic cancer, prostate cancer, endometrial cancer) will be studied with a single blood test for comparison.

Towards utilising the blood test as a means of discriminating between patients with colorectal cancer and those without we wish to obtain blood samples from 300 patients in primary care with colorectal symptoms and compare the test result (positive, equivocal or negative) with their final diagnosis (colorectal cancer or benign pathology). The blood test results will not be revealed to the GP or the patient so cannot influence the current referral pathway until the blood test is validated for this patient population. We will use this data to plan a subsequent interventional study.

